6.1. Adverse Event Reporting

The Common Terminology Criteria for Adverse Events (CTCAE) version 4.0 will be used for grading of all adverse events.

(<http://evs.nci.nih.gov/ftp1/CTCAE/About.html>)

An adverse event is defined as any unfavorable and unintended change in the structure or function of the body temporally associated with the treatment. Any worsening (i.e., any clinically significant adverse change in frequency and/or intensity) of a preexisting condition which is temporally associated with treatment, is also an adverse experience.

In the event of an adverse event the first concern will be for the safety of the subject. All subjects/patients with serious adverse experiences must be followed up for outcome.

Serious Adverse Experiences are:

Any untoward medical occurrences that at any dose:

- Results in death,
- Is life-threatening,
- Requires inpatient hospitalization or prolongation of existing hospitalization,
- Results in persistent or significant disability/incapacity

Medical and scientific judgment should be exercised in deciding whether expedited reporting is appropriate in other situations, such as important medical events that may not be immediately life-threatening or result in death or hospitalization but may jeopardize the patient or may require intervention to prevent one of the other outcomes listed in the definition above. These should also usually be considered serious.

If disease progression is noted during a protocol-specified reevaluation of the status of a patient's cancer, and the progression is manifested solely by result of radiologic imaging, that occurrence of progressive disease will NOT be recorded as an adverse experience.

Each occurrence of a given adverse event will be recorded. Only the most severe grade over the course of a given episode will be recorded.

Serious adverse events occurring after a patient is discontinued from the study will NOT be reported unless the investigator feels that the event may have been caused by a protocol procedure. Study-specific clinical outcomes of death because of disease progression are exempt from serious adverse event reporting, unless the investigator deems them related to a protocol procedure.

In general, serious adverse events assessed as clearly being due to disease progression and not due to a protocol procedure should be excluded from adverse event reporting.

However, in cases where the specificity or severity of an event is not consistent with the risk information, the event should be reported.

All STEAEs will be recorded on Adverse Events Communication Form and reported to:

- 1) Study Coordination Center/Principal Investigator
Stanford University/ [name]

- 2) Stanford University Cancer Clinical Trials Office (Study Coordination Center)
Stanford University Cancer Center
Administrative Panels Office
Stanford University, [name]

RETENTION OF RECORDS

All documentation of adverse events and all IRB correspondence will be retained for at least 2 years after the investigation is completed.

7. CORRELATIVE/SPECIAL STUDIES

N/A

8. STUDY CALENDAR

Parameters	Pre-Entry	1 month ^a	6 month ^e	12 month ^e
History/ Physical Exam	X	X	X	X
KPS	X	X	X	X
HRQOL ^b	X	X	X	X
Labs ^c	X			
Brain MRI or CT ^d	X	X	X	X
Steroid use Assessment	X	X	X	X
Toxicity Evaluation		X	X	X
	^a ± 7 days			

	
^b EORTC-QLQ C30 and BN-20, MDASI-BT
 
^c Laboratory tests: complete blood count, general chemistry panel, and comprehensive metabolic panel
 
^d MRI schedule may change as indicated should patient have clinical deterioration; CT instead of MRI is acceptable if patient has pacemaker.
 
^e ± 1 month

--	---

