1. OBJECTIVES

1.1.Phase I - Primary Objective

- 1.1.1 Determine the maximum tolerated dose (MTD), based on acute CNS toxicity at 30 days, of hypofractionated radiotherapy given in 5 fractions with temozolomide for the treatment of glioblastoma multiforme.

1.2.Secondary Objectives

- 1.2.1. Assess the short- and long-term adverse effects.
- 1.2.2. Determine the radiographic response rate.
- 1.2.3. Determine the overall survival rate.
- 1.2.4. Determine the patterns of tumor failure.
- 1.2.5. Assess quality of life during treatment.

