1.2.7. Dose definition and administration

Oral temozolomide (75 mg/m²/day) will be administered daily during radiotherapy. The first dose of temozolomide will begin the day before the first fraction of radiation. The last dose will be taken the day of the last fraction of radiation. Following radiotherapy, maintenance temozolomide will be prescribed at the discretion of the treating neuro-oncologist.

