4.5.7. Recall blisters post-sun exposure can be treated with Domeboro soaks. If neuropathy occurs, patients may be placed on gabapentin.

4.5.8. No other chemotherapy treatment is permitted during protocol treatment.

4.6 **Duration of Therapy**

The first dose of temozolomide will begin the day before the first fraction of radiation. It will be taken through the day of the last fraction of radiation. Following radiotherapy, maintenance temozolomide will be prescribed at the discretion of the treating neuro-oncologist.

4.7 **Duration of Follow Up**

Patient follow-up schedule is summarized under section 8. Study Calendar.

The following will be obtained at pre-treatment evaluation and at each follow-up time points: Neurologic history and physical examination, KPS, steroid use assessment, and toxicity evaluation (see Follow-up assessment form). MRI with gadolinium will be obtained pre-treatment and at 1, 6, and 12 months following treatment until progression is documented.

In addition to the follow-up schedule outlined in section 8, additional clinical follow-up and MRI scans will be obtained based on clinical progress during the first 12 months following radiation.

After the first 12 months or after the documentation of disease progression, patients will be followed every 3-6 months at the discretion of the treating physician.

For those subjects who are unable to come for clinic visits, clinical follow-up information will be obtained via 1) a phone call to the patient and/or 2) clinic source document from his/her local physician. For patients unable to return to for imaging studies, source documents from outside institutions will be used to document imaging follow-up.

4.8 **Criteria for Removal from Study**

- Disease progression or death
- Intercurrent illness that prevents further administration of treatment: a condition, injury, or disease unrelated to cancer, that renders continuing temozolomide or radiation treatment unsafe or regular study visits impossible, including, but not limited to, active infection, symptomatic congestive heart failure, unstable angina pectoris, cardiac arrhythmia, pregnancy, or psychiatric illness that would limit compliance with study requirements.
- Unacceptable adverse event(s) (see adverse events)
- Patient decides to withdraw from the study
- General or specific changes in the patient's condition that render the patient ineligible for the study

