6. ADVERSE EVENTS AND REPORTING PROCEDURES

6.1 Potential Adverse Events

6.1.1. Radiation

6.1.1.1. Early, < 30 days from treatment: Expected adverse events include fatigue, alopecia, skin erythema, serous otitis, radiation pharyngitis, headache, neck pain, nausea and vomiting, and lethargy.

6.1.1.2. Late, > 30 days from treatment: Possible adverse events include focal neurologic deficits, memory difficulties, dementia, radiation necrosis, and radiation induced neoplasms.

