9. MEASUREMENT OF EFFECT

9.1 Anti-tumor Effect

Brain MRI will be obtained at 1st, 6th, and 12th months following radiotherapy until disease progression. Patients may require imaging prior to the study defined assessment points should clinical deterioration warrant; should this occur, effort will be made to return to the protocol defined imaging schedule. However, clinical evaluation by the treating physicians may warrant an altered schedule. After the first year or after the documentation of disease progression, brain MRI will be obtained every 3-6 months at the discretion of the treating physician.

For patients unable to return to for imaging studies, source documents from outside institutions will be used to document imaging follow-up.

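### No toxicity evaluation is scheduled from pre-entry until about day 23-37 after radiotherapy, so transient, mainly low-grade acute events may be under-ascertained

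*Combined protocol and SAP*

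**What the plan says.** The section 8 calendar has four columns: pre-entry, 1 month (± 7 days), 6 months and 12 months (each ± 1 month). The "Toxicity Evaluation" row is marked in the last three only. Section 4.7 introduces its own assessment list, which includes toxicity, with "The following will be obtained at pre-treatment evaluation and at each follow-up time points". Neither place schedules grading during or at the end of radiotherapy. The two also disagree on pre-treatment toxicity evaluation: section 4.7 lists it, while the calendar cell is blank.

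The exposure falls inside this gap. Radiation is given in five fractions, and section 4.4 states "Oral temozolomide (75 mg/m²/day) will be administered daily during radiotherapy", starting the day before the first fraction and ending with the last.

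For early radiation effects, section 6.1.1.1 says "Expected adverse events include fatigue, alopecia, skin erythema, serous otitis, radiation pharyngitis, headache, neck pain, nausea and vomiting, and lethargy". Objective 1.2.1 is to "Assess the short- and long-term adverse effects", and section 11.1.2 repeats this as an endpoint.

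Two provisions operate outside the calendar. Section 6.1 (Adverse Event Reporting) says "Each occurrence of a given adverse event will be recorded", with the worst grade of each episode. Section 4.7 says "additional clinical follow-up and MRI scans will be obtained based on clinical progress during the first 12 months following radiation".

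**The concern.** The acute window in section 4.3 covers fewer than 30 days from the end of radiotherapy. Most of it, and all of the treatment, passes before anyone is scheduled to grade toxicity. Several of the expected early effects can start and resolve in that time. Recording the worst grade of an episode is harder weeks after it has ended.

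What is mainly at stake is the short-term adverse-effect endpoint: a description of acute tolerability that depends on which events happened to be mentioned or noted. The error would run one way, because events that are missed can only make the regimen look better tolerated.

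The protocol also seems to expect assessment around treatment. Objective 1.2.5 concerns quality of life while treatment is under way, and section 4.5.1 ties steroid-dose recording to treatment evaluations. The calendar has no such visit.

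**Working it through.** **Inputs.** The 1-month visit tolerance is ± 7 days (section 8). Follow-up months are counted from radiotherapy: section 9.1 has "Brain MRI will be obtained at 1st, 6th, and 12th months following radiotherapy until disease progression". Temozolomide starts one day before the first fraction (section 4.4). Fraction spacing is not stated; five consecutive days is assumed here.

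**1. When the first scheduled grading falls.** With 1 month = 30 days: 30 − 7 = 23 and 30 + 7 = 37, so day 23-37 after the end of radiotherapy. A 28-day month gives 21-35 and a 31-day month 24-38.

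**2. How far back that visit must look.** From the first fraction, add 4 days: 27-41. From the first temozolomide dose, add 5 days: 28-42. If a weekend interrupts the fractions, add 7 days: 30-44. A visit on day 23 also leaves days 24-29 of the acute window (29 − 23 = 6 days) without a scheduled evaluation until month 6.

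**3. Whether anything else covers the interval.**
- Section 6.1 sets what to record (every occurrence, worst grade, CTCAE v4.0). It does not say when or how non-serious events are elicited.
- The additional follow-up in section 4.7 is triggered by clinical progress, so it does not collect transient events systematically.
- In Appendix B, the Initial Consult Form has no toxicity item. The Follow-up Form asks for a grade and for the relation of CNS toxicity to treatment, and shows no onset date.

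**4. Which events are exposed.** The table in section 6.1.2 gives counts for temozolomide plus conventional radiotherapy (n = 288):

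| Event | All | Grade ≥3 | Below grade 3 |
|---|---|---|---|
| Nausea | 105 | 2 | 103 |
| Vomiting | 57 | 1 | 56 |
| Headache | 56 | 5 | 51 |
| Convulsions | 17 | 10 | 7 |
| Confusion | 11 | 4 | 7 |

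The first three are nearly all below grade 3, and that table does not class them as CNS events. The CNS rows have a much larger severe share (10/17 and 4/11). The risk therefore falls mainly on the low-grade, non-CNS profile.

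**5. Illustrations only.** The documents state no capture rate, so no estimate is possible. Let s be the assumed share of events captured.
- Nausea among 15 patients (the stated maximum per arm): 15 × 105/288 = 5.5 cases. With s = 0.9, 0.7 and 0.5 this becomes 4.9, 3.8 and 2.7. The rate comes from a regimen that section 4.5.4 describes as 42 days long, so it may not apply to five fractions.
- A dose level passes the 3+3 table with probability (1 − q)³ + 3q(1 − q)⁵, where q = p × s and p is the true rate of dose-limiting toxicity. With p = 0.30 and s = 1, this is 0.343 + 0.151 = 0.494. With s = 0.75, q = 0.225 and it is 0.465 + 0.189 = 0.654. Both p and s are assumed. This shows the direction of the effect and does not estimate its size.

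**The case against.** The strongest reply is that a missing calendar column is not missing ascertainment. The duty in section 6.1 to record each occurrence is not tied to calendar visits. Patients attend for every fraction, so staff bound by that duty see them during treatment. Section 4.7 allows extra visits and, for patients who cannot attend, telephone contact or local physicians' records. Section 4.8 requires treatment-related toxicities and serious events to be followed to resolution. Serious events have their own reporting route.

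Much of this stands. A reader might infer that acute toxicity is graded from recall, or that transient events are in fact under-counted. The documents say neither: events can be recorded when they occur, and no evidence on capture is given. They support only a risk.

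A reader might also infer that the gap biases escalation and the maximum tolerated dose. That is not established. A dose-limiting toxicity is a treatment-related grade 3-5 CNS event. Such events are the least likely to go unnoticed (a judgement), and many would meet the serious-event criteria. The risk is not nil: with three to six patients per level, one missed event can turn 1 of 3 into 0 of 3. The pass probabilities above, however, rest wholly on assumed rates.

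The reply does not supply a time or method for eliciting non-serious events before the 1-month visit. It is also right that a last-fraction assessment does not by itself cover the three weeks after radiotherapy, so the fix needs a second part.

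**Conclusion.** The point holds as a gap in scheduled ascertainment. Nothing is scheduled between pre-entry and about day 23-37 after radiotherapy, and the general recording rule does not say how that interval is covered. Transient, mainly low-grade acute events may be under-ascertained, which weakens objective 1.2.1 and the matching endpoint in section 11.1.2. Any effect on the maximum tolerated dose is secondary and cannot be sized from the documents.

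The day range assumes a 30-day month and visits counted from the end of radiotherapy. The longer look-back figures also assume a fraction spacing. No sample-size figure is affected. This is an inexpensive improvement to data collection, worth making because acute toxicity is what the trial sets out to describe.

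**What to change.** 1. Add a last-fraction column to the section 8 calendar with a CTCAE v4.0 toxicity evaluation and the steroid dose that section 4.5.1 asks for at treatment evaluations. Complete it at the existing treatment visit on the Appendix B Follow-up Form, using its box for other time points, and count its grades as acute.
2. At the 1-month visit, record the onset date and worst grade of every event since the last fraction. This covers the weeks after radiotherapy and needs an onset-date field on the form.
3. Reconcile section 4.7 with the calendar on whether toxicity is assessed before treatment.

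The cost is one extra form and a few minutes of clinic time per patient, with no new visit or test. The change does not detect asymptomatic laboratory toxicity, because the calendar marks labs at pre-entry only. The post-radiotherapy interval would still be graded retrospectively at 1 month, but in a structured way.

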9. MEASUREMENT OF EFFECT

9.1 Anti-tumor Effect

Brain MRI will be obtained at 1st, 6th, and 12th months following radiotherapy until disease progression. Patients may require imaging prior to the study defined assessment points should clinical deterioration warrant; should this occur, effort will be made to return to the protocol defined imaging schedule. However, clinical evaluation by the treating physicians may warrant an altered schedule. After the first year or after the documentation of disease progression, brain MRI will be obtained every 3-6 months at the discretion of the treating physician.

For patients unable to return to for imaging studies, source documents from outside institutions will be used to document imaging follow-up.

9.1.2 Disease Parameters

Local tumor progression is defined as the radiographic appearance of a new or increasing enhancing lesion within the radiosurgical target volume. Patients with increased tumor size on MRI may continue on the protocol until true tumor progression (i.e., not pseudo-progression) is determined by the treating physicians.

9.1.3 Methods for Evaluation of Measurable Disease

9.1.4 Response Criteria

The primary measure of response will be by serial measures of the product of the two largest cross-sectional diameters. Response will also be evaluated in this study using the [following](#) criteria:

9.1.4.1 Complete response (CR): Circumstance when the enhancing tumor is no longer seen by neuroimaging.

9.1.4.2 Partial response (PR): Decrease of >50% in the product of the two greatest diameters on the follow-up MRI scan. No new lesions may appear. The dose of dexamethasone must be the same or lower than at baseline.

9.1.4.3 Minor response (MR): Decrease of <50% in the product of the two greatest diameters on the follow-up MRI scan. Neither partial response or progressive disease.

9.1.4.4 Progression (P): A >25% increase in tumor area (product of the two greatest diameters) provided that the patient has not has a decrease in steroid dose since the last evaluation period. A concomitant decrease in steroid dose will rule out a progression designation during the first 2 months after the completion of XRT.

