Several groups have employed hypofractionated radiotherapy alone, without chemotherapy, for treatment of high grade glioma and have shown hypofractionated RT to be well tolerated. Thomas has shown the regimen of 30 Gy in 5 Gy fractions was without acute toxicity(13). Floyd *et al.* delivered 50 Gy in 5 Gy fractions over a 2-week course. While 3 of 20 patients in this study underwent surgical re-excision due to radiation necrosis, these three patients also enjoyed longer survival (range, 9-23 months)(14). Hulshof compared conventional fractionation with hypofractionation using 66 Gy in 2 Gy (conventional fractionation), 40 Gy in 5 Gy, and 28 Gy in 7 Gy fractions. Patients treated with the conventional radiation schedule had similar median survival as the 28 Gy in 7 Gy fraction group despite having patients with significantly worse prognostic factors in the hypofractionation group(15). In a prospective trial of patients older than 60 years, a shorter course of radiotherapy, using 40 Gy in 15 fractions (2.67 Gy fractions) over 3 weeks, decreased treatment time and corticosteroid requirement without negatively affecting survival when compared to conventional radiotherapy (60 Gy in 2 Gy fractions over 6 weeks)(16).

A major concern of using high doses per fraction is the potential for neurotoxicity. Multiple studies have demonstrated doses ranging from 2.5 to 7 Gy per fraction to be well tolerated in patients without prior radiation(13, 17-19). Hypofractionated radiotherapy has also been shown to be safe in patients with prior radiation: In a study by Hudes and colleagues, patients with recurrent or persistent malignant glioma who had previously received a median dose of 60 Gy (range, 44 – 72 Gy) of external beam radiation were treated with stereotactic radiotherapy to target recurrent or persistent tumors in a phase I dose escalation study. Although there was no tumor response to 24 Gy in 3 Gy fractions, 79% responded to 30 Gy in 3 Gy or 35 Gy in 3.5 Gy fractions. There was no grade ≥ 3 toxicity, and no patient required a re-resection due to toxicity(20). Shepherd *et al.* reported hypofractionated stereotactic radiotherapy in treatment of recurrent glioma using 5 Gy fractions to total doses ranging from 20 to 50 Gy to be well tolerated, with 36% having reversible steroid-dependent toxicity and only 6% requiring reoperation(21).

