4.5 General Concomitant Medication and Supportive Care Guidelines

All supportive therapy for optimal medical care will be given during the study period at the discretion of the attending physician(s) within the parameters of the protocol.

- 4.5.1. Steroids may be given as clinically indicated. The total dose must be recorded pretreatment and at the time of each treatment evaluation. Steroids will be used in the smallest dose that will afford the patient satisfactory neurologic function and the best possible quality of life.
- 4.5.2. Antiemetics: Patients may be given antiemetics prior to each daily dose of temozolomide. The antiemetic and dosing will be left to the treating physician's discretion. Other antiemetics such as 5HT3 antagonists or lorazepam (Ativan®) may be used at the discretion of the investigator for late nausea and vomiting.
- 4.5.3. Anticoagulants: Patients who are taking warfarin (Coumadin®) may participate in this study; however, it is recommended that international normalization ration (INR) or prothrombin time be monitored carefully. The frequency of INR determinations is left to the clinical judgment of the investigator. Subcutaneous heparin or fractionated heparin products are also permitted.
- 4.5.4. Pneumocystis prophylaxis: Prophylaxis against *Pneumocystis carinii* pneumonia is typically recommended for all patients receiving concomitant temozolomide and radiotherapy for the 42-day regimen. Since the duration of radiotherapy/temozolomide regimen is shorter on this protocol, the use of pneumocystis prophylaxis is left to the clinical judgment of the investigator. All patients receiving temozolomide, particularly patients receiving steroids, should be observed closely for the development of *Pneumocystis* pneumonia. Acceptable regimens are:

4.5.4.1. *Trimethoprim-sulfamethoxazole*: Trimethoprim will be given at 160 mg/sulfamethoxazole 800 mg daily for 3 days each week, beginning on day 1 of radiation therapy and continuing for 14 days after completion of radiation therapy.

4.5.4.2. For subjects allergic to sulfa compounds, pentamidine (or dapsone or atovaquone) may be the drug used. The choice is left to the discretion of the investigator.

4.5.5. Infections are to be treated with the appropriate antibiotics and recorded.

4.5.6. Analgesics and any other medications are to be specified and their doses recorded.

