QOL Forms: EORTC QLQ-C30 + BN-20 MDASI-BT		Date: _____	
Decadron		 No/  Yes; Dose _____	
Brain MRI Date: _____		Protocol Lesion Size (from treatment plan): Volume _____ mL Measurement (2 greatest cross sectional diameters): _____ mm x _____ mm = _____ Final PTV size: _____ mL	

**Protocol ID: Hypofractionated Radiotherapy for Treatment of GBM
Patient Follow-up Form**

Date of follow-up visit: _____ **Treatment Date:** _____

Study Arm: #1: PTV <60mL #2: PTV 60-150mL

Dose Level: 25Gy 30Gy 35Gy 40Gy

Patient Number on this Dose Level: _____

Follow-up time:

1 month; 6 months; 12 months; Other: _____

	Done	If done:	Not Done
KPS Assessment		KPS: _____	
QOL Forms: EORTC QLQ-C30 + BN-20 MDASI-BT		Date: _____	
Decadron		 No  Yes; Dose _____	
Brain MRI Date: _____		Protocol Lesion Size (from current MRI): Measurement (2 greatest cross sectional diameters): _____ mm x _____ mm = _____ Assessment (see below):  Complete Response  Partial Response  Minor Response  Progression	
Toxicity Evaluation		 NONE  Toxicity Present (Grade per CTCAE): CNS Toxicity is related to Protocol Treatment:  Not applicable  Yes  No	

Comments / Notes:

Date of next follow-up visit: _____

Orders for next follow-up visit:

1 month F/U	6 month F/U	12 month F/U	Other
MRI @ 1 mo	MRI @ 6 mo	MRI @ 12 month	

MRI

Assessment:

Complete response (CR): Circumstance when the enhancing tumor is no longer seen by neuroimaging.

Partial response (PR): Decrease of >50% in the product of the two greatest diameters on the follow-up MRI scan. No new lesions may appear. The dose of dexamethasone must be the same or lower than at baseline.

Minor response (MR): Decrease of <50% in the product of the two greatest diameters on the follow-up MRI scan. Neither partial response or progressive disease.

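### Complete response lacks the steroid condition that partial response carries, and no response category says how to score a scan after re-excision of the target lesion

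*Combined protocol and SAP*

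**What the plan says.** Section 9.1.4 of the protocol has four response categories.

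- **Complete response (9.1.4.1)** has a single criterion, on imaging: "Circumstance when the enhancing tumor is no longer seen by neuroimaging".
- **Partial response (9.1.4.2)** needs a decrease of more than 50% in the product of the two greatest diameters, no new lesions, and a steroid condition: "The dose of dexamethasone must be the same or lower than at baseline".
- **Minor response (9.1.4.3)** reads: "Decrease of <50% in the product of the two greatest diameters on the follow-up MRI scan. Neither partial response or progressive disease".
- **Progression (9.1.4.4)** is an increase of more than 25%, "provided that the patient has not has a decrease in steroid dose since the last evaluation period".

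The follow-up form in Appendix B repeats the definitions, including "Complete response (CR): Circumstance when the enhancing tumor is no longer seen by neuroimaging", and offers one tick box for each of the four categories. It has a field for Decadron dose but none for re-operation.

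On steroids, section 4.5.1 says "Steroids may be given as clinically indicated", requires the smallest dose that keeps neurologic function and quality of life satisfactory, and adds: "The total dose must be recorded pretreatment and at the time of each treatment evaluation".

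Section 6.1.1.2 lists radiation necrosis as a possible late event. The background on hypofractionated radiotherapy says of one series: "While 3 of 20 patients in this study underwent surgical re-excision due to radiation necrosis". The radiographic response rate is a secondary objective (1.2.2) and a secondary endpoint (11.1.2).

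**The concern.** Steroid dose enters the definitions of partial response and progression, so the protocol itself treats it as something that can distort the reading of the enhancing lesion. The top category has no such condition. A change that is not accepted as a partial response on raised dexamethasone is accepted as a complete response if it goes further.

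The second gap concerns surgery and is not specific to complete response. None of the four categories says what to do with a scan taken after the target lesion has been removed following protocol radiotherapy. Read literally, an operation for a radiation complication can produce the imaging finding that defines complete response.

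At stake is what the reported response rate means. It is a secondary result in small arms, where one or two patients change the figure visibly.

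**Working it through.** There is no planned figure to reproduce, because the point concerns a definition. The first two steps apply the text to cases; the third gives scale.

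**1. Steroid route.** Take two patients with measurable enhancing tumor at baseline, both on more dexamethasone than at baseline when scanned.

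| | Decrease in product | Complete (9.1.4.1) | Partial (9.1.4.2) | Minor (9.1.4.3) | Progression (9.1.4.4) |
|---|---|---|---|---|---|
| Patient A | 60% | No, enhancement remains | No, dose above baseline | No, decrease is not below 50% | No |
| Patient B | 100% | Yes | not needed | not needed | No |

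Patient B is scored in the highest category. Patient A fits none of the four boxes unless the second sentence of the minor response definition is read as a catch-all, which its first sentence contradicts.

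**2. Surgery route.** A patient has residual enhancing tumor after partial resection or biopsy. After radiotherapy the lesion enlarges. Section 9.1.2 lets the patient continue if the physicians judge that this is not true progression. The lesion is then re-excised and found to be necrosis. If the next scan shows no enhancement, the wording of 9.1.4.1 is met. Nothing in 9.1.4, 9.1.2, 4.7, section 11 or the form excludes that scan or scores it separately.

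**3. Scale.** Inputs:

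- Arm size: 15, the maximum stated in 11.2.1.
- Re-excision for necrosis: 3/20 = 15%, in the cited series of 50 Gy in 5 Gy fractions.
- Re-operation: 6%, in the cited recurrent-glioma series.
- Patients with residual enhancing tumor: not given. 8 of 15 is used as an assumption.

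Results:

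- Shift per misscored patient: 1/15 = 6.7 points. If the rate is taken over only the 8 assumed to have residual tumor, 1/8 = 12.5 points.
- Expected re-operations per 15 patients: 0.06 × 15 = 0.9 to 0.15 × 15 = 2.25.
- Expected among the 8: 0.06 × 8 = 0.48 to 0.15 × 8 = 1.2, or about 0.5 to 1.2.

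These counts are re-operations. A false complete response also needs surgery that leaves no enhancement, and a later scan that is scored for response. Even if the cited rates applied, the counts are therefore upper bounds. No calculation is possible for the steroid route: the 36% cited in the recurrent-glioma series is steroid-dependent toxicity, not disappearance of enhancement.

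**The case against.** The strongest case on the other side is that this is a small clarification to a descriptive endpoint in a 3+3 phase I trial. Steroid dose is recorded beside the response box, so complete responses on raised steroids could be identified at reporting. Section 9.1.4 names the serial diameter product as the primary measure of response, with the categories as an additional evaluation. An enlarging necrotic lesion might be called progression before any surgery, and progression is a removal criterion in 4.8.

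Much of this stands as a limit on importance, but it does not close the gap. Recording the dose makes a correction possible; no rule tells anyone to make it. The serial product has no steroid or surgery rule either, and falls to zero in the same cases. The progression route fails in the very case at issue, where enlargement is judged not to be true progression and the patient stays on protocol under 9.1.2.

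A reader might infer several stronger things that the documents do not support:

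- *That steroid use is unrestricted.* Section 4.5.1 requires the smallest satisfactory dose and a record at each evaluation.
- *That 0.9 to 2.25 false complete responses per arm are to be expected.* Those are re-operation counts, from a regimen without chemotherapy and with a different fractionation (15%) and from recurrent disease (6%).
- *That the error would concentrate at higher doses or in the larger-PTV arm and mimic a dose-response.* This is plausible, but no passage gives rates by dose or volume, and no comparison of response by dose or arm is planned.
- *That a patient who is both a late DLT and a complete response exposes a contradiction.* Toxicity and response are separate endpoints, and scoring one does not stop the other being graded.
- *That a best overall response is inflated.* The protocol defines no best response; complete response is only the top category.

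**Conclusion.** The concern holds as two defects of endpoint definition. The steroid condition on partial response is missing from complete response, an inconsistency within one section that needs no assumption to establish. The absence of a rule for scans after re-excision affects every category.

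The consequence is limited to the radiographic response rate. The MTD, the DLT definition, the escalation rules and survival are unaffected. Each misscored patient is worth 6.7 points in an arm of 15. How many there would be is unknown. For the surgery route, the bound of 0.9 to 2.25 re-operations per 15 (about 0.5 to 1.2 with 8 of 15 having residual tumor) assumes that rates from other regimens and populations apply here. For the steroid route there is no rate at all. The change is worth making because the definition is inconsistent and cheap to repair, not because a large bias has been shown.

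**What to change.** The changes concern endpoint scoring only and leave clinical management as it is. In 9.1.4 and on the Appendix B follow-up form:

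1. Apply the dexamethasone condition of partial response to complete response.
2. Add a box for any decrease of 50% or more on dexamethasone above baseline, labelled for example *not a response (steroid increased)*. Without it, extending the condition would leave Patient B, like Patient A, with no category.
3. Score response as not evaluable from the date of any post-radiotherapy resection of the target lesion, and keep earlier assessments as recorded. Carrying the last pre-surgery category forward would be worse: it could fix a progression that was really necrosis or, with scheduled scans at 1, 6 and 12 months, rest on an old reading.
4. Add one checkbox for re-operation.

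The cost is a few sentences in 9.1.4 and two small additions to the form. Steroid dose is already collected. The downside is that the reported complete response rate may fall.
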